6.3. DERIVED TIMEPOINTS

The last non-missing post-Baseline (i.e., post-first dose) measurement collected during the study up to and including the Visit 10 (EOT/ET) measurement will be carried forward and defined as the last observation carried forward (LOCF) endpoint. Both scheduled and unscheduled assessments as well as the early termination assessments that are collected during this period will contribute to the derivation of the LOCF endpoint. However, unscheduled measurements taken after the Visit 10 (EOT/ET) measurement will not be used in the derivation.

The LOCF endpoint will be derived for the following outcome measures:

- PANSS: total score, subscale scores, Marder factor scores, UPSM factor scores and total factor score, individual item scores, and derived binary variables for PANSS response. For a given subject, the LOCF values for all PANSS summary and individual item scores and derived binary variables should come from the same assessment and it should be the last post-Baseline assessment up to and including Visit 10 where PANSS total score is available. In the rare event where no PANSS total score is available after first dose due to partially completed assessments, the last post-Baseline assessment up to and including Visit 10 should be taken as the LOCF assessment for all raw and derived scores as applicable.
- CGI-S score.
- BNSS: total score, subscale scores, and individual item scores. For a given subject, the LOCF values for all BNSS summary and individual item scores should come from the same assessment and it should be the last post-Baseline assessment up to and including Visit 10 where BNSS total score is available. In the rare event where no BNSS total score is available after first dose due to partially completed assessments, the last post-Baseline assessment up to and including Visit 10 should be taken as the LOCF assessment for all raw and derived scores as applicable.
- SF-12.
- PSP: total score, individual domain scores, and the derived binary variables. For a given subject, the LOCF values for all PSP data should come from the same assessment and it should be the last post-Baseline assessment up to and including Visit 10 where PSP total score is available. In the rare event where no PSP total score is available after first dose due to partially completed assessments, the last post-Baseline assessment up to and including Visit 10 should be taken as the LOCF assessment for all raw and derived scores as applicable.
- MSQ score.
- C-SSRS suicidal ideation score (0-5).

Document:

PPD

Author:

PPD

Version Number:

1.0

Version Date:

06MAY2024

- SAS: mean score and individual item scores. For a given subject, the LOCF values for all SAS summary and individual item scores should come from the same assessment and it should be the last post-Baseline assessment up to and including Visit 10 where SAS mean score is available. In the rare event where no SAS mean score is available after first dose due to partially completed assessments, the last post-Baseline assessment up to and including Visit 10 should be taken as the LOCF assessment for all raw and derived scores as applicable.
- BARS: total score and individual item scores. For a given subject, the LOCF values for all BARS summary and individual item scores should come from the same assessment and it should be the last post-Baseline assessment up to and including Visit 10 where BARS total score is available. In the rare event where no BARS total score is available after first dose due to partially completed assessments, the last post-Baseline assessment up to and including Visit 10 should be taken as the LOCF assessment for all raw and derived scores as applicable.
- AIMS: total score and individual item scores. For a given subject, the LOCF values for all AIMS summary and individual item scores should come from the same assessment and it should be the last post-Baseline assessment up to and including Visit 10 where AIMS total score is available. In the rare event where no AIMS total score is available after first dose due to partially completed assessments, the last post-Baseline assessment up to and including Visit 10 should be taken as the LOCF assessment for all raw and derived scores as applicable.
- PSQI: global score, component scores, and individual item scores. For a given subject, the LOCF values for all PSQI summary and individual item scores should come from the same assessment and it should be the last post-Baseline assessment up to and including Visit 10 where PSQI global score is available. In the rare event where no PSQI global score is available after first dose due to partially completed assessments, the last post-Baseline assessment up to and including Visit 10 should be taken as the LOCF assessment for all raw and derived scores as applicable.
- CGI-I.
- Clinical laboratory parameters (blood chemistry, hematology, urinalysis, HOMA-IR (if collected)). For a given subject, the LOCF values for the clinical laboratory parameters do not have to all come from the same assessment; the only exception is: the LOCF flag for the counts of leukocytes and its differential should be applied to records from the same assessment and it should be the last post-Baseline assessment up to and including Visit 10 where counts of leukocytes and its differential are reported. LOCF endpoint does not need to be derived for RBC morphology findings, WBC morphology findings, and urinalysis microscopic examination findings (excluding urine erythrocytes and leukocytes).
- Urine drug screening: For a given subject, the LOCF values for all urine drug screening parameters should come from the same assessment and it should be the last post-Baseline assessment up to and including Visit 10 where a urine drug screening test was administered.
- Vital sign parameters (supine and standing SBP, supine and standing DBP, supine and standing pulse rate, respiratory rate, oral temperature), weight, BMI, and waist circumference. For a given subject, the LOCF values for all vital sign parameters, height, weight, BMI, and waist circumference do not have to come from the same assessment; the only exceptions are: (1) the LOCF flag for weight and BMI should be applied

Document: PPD

Author: PPD

Version Number:

1.0

Version Date:

06MAY2024

to records from the same assessment and it should be the last post-Baseline assessment up to and including Visit 10 where weight is available (2) the LOCF flag for supine SBP and DBP, standing SBP and DBP, and the derived corresponding orthostatic endpoints (i.e., standing SBP – supine SBP; standing DBP – supine DBP) should be applied to records from the same assessment and it should be the last post-Baseline assessment up to and including Visit 10 where all four BP measures are available, (3) the LOCF flag for supine and standing pulse rate and the derived corresponding orthostatic endpoint (i.e., standing pulse rate – supine pulse rate) should be applied to records from the same assessment and it should be the last post-Baseline assessment up to and including Visit 10 where both pulse rate measures are available.

- ECG parameters: For a given subject, the LOCF values for all ECG parameters do not have to come from the same assessment. LOCF endpoint does not need to be derived for ECG parameters in the category of "FINDING".
- Nicotine use data: LOCF of this outcome measure should come from the same assessment and it should be the last assessment post first dose up to and including Visit 10 where any data are reported.
- Healthcare resource utilization data: LOCF of this outcome measure should come from the same assessment and it should be the last assessment post first dose up to and including Visit 11 where any data are reported.

The study visits will be mapped to analysis visits for table summaries and statistical analyses where applicable (Table 1).

Table 1: Mapping of study visits to analysis visits.

Study Visit	Analysis Visit Number	Analysis Visit
Visit 1	1	Screening/Visit 1
Visit 2	2	Pre-switch Baseline/Visit 2
Visit 3	3	Week 1/Visit 3
Visit 4	4	Week 2/Visit 4
Visit 5	5	Week 3/Visit 5
Visit 6	6	Week 4/Visit 6
Visit 7	7	Week 5/Visit 7
Visit 8	8	Week 6/Visit 8

Document: PPD

Author: PPD

Version Number:

1.0

Version Date:

06MAY2024

Study Visit	Analysis Visit Number	Analysis Visit
Visit 9	9	Week 7/Visit9
Visit 10 (if representing true EOT visit). For ET visit mapping see Section 6.4 .	10	Week 8/Visit 10
Visit 11	11	Week 9/Follow-up/Visit 11

Original study visit collected on the case report forms (CRFs) will be displayed in the listings.

6.4. RETESTS, UNSCHEDULED VISITS, AND EARLY TERMINATION DATA

In general, for by-visit summaries, data recorded at the planned visits where assessment is intended to be given will be presented, as well as the derived Baseline value and the LOCF value.

Unscheduled measurements will not be included in by-visit summaries as a separate time point. Unscheduled measurements collected prior to the first dose of study medication will contribute to the derivation of the Baseline value. Unscheduled measurements collected post Baseline will contribute to the derivation of the LOCF value, the potential clinically significant (PCS) value, and the best/worst case value where required (e.g., shift table).

In the case of a retest, the assessment recorded under the planned visit will be used for by-visit summaries, and the assessment(s) recorded under unscheduled visit(s) will be presented in listings only.

As per protocol, study Visit 10 can be a Week 8/End of Treatment (EOT) visit or an Early Termination (ET) visit. If a subject terminates early, his/her measurements taken at the ET visit will be mapped to the next planned visit (after the last scheduled visit the subject attended) during which that assessment was expected to be performed as specified by the Schedule of Assessments table in the protocol. This applies to both safety and effectiveness data.

Listings will include scheduled, unscheduled, retest and early discontinuation data with original dates and visits displayed.

6.5. WINDOWING CONVENTIONS

No visit windowing will be performed during the analysis for this study. Data will be analyzed according to the schedule outlined in the CSP.

Document: PPD

Author: PPD

Version Number:

1.0

Version Date:

06MAY2024

6.6. STATISTICAL TESTS

The default significance level will be 5%; confidence intervals (CIs) will be 95%. All CIs will be two-sided, unless otherwise specified in the description of the analyses or the outputs.

6.7. COMMON CALCULATIONS

For quantitative measurements, change from Baseline will be calculated as:

- Test Value at Visit X - Baseline Value

For PANSS total score, percentage change from Baseline will be calculated as:

- $(\text{Test Value at Visit X} - \text{Baseline Value}) \times 100 / (\text{Baseline Value} - 30)$

For other quantitative measurements, percentage change from Baseline will be calculated as:

- $(\text{Test Value at Visit X} - \text{Baseline Value}) \times 100 / \text{Baseline Value}$

6.8. SOFTWARE VERSION

All analyses will be conducted using SAS version 9.4 or later.

7. STATISTICAL CONSIDERATIONS

7.1. ADJUSTMENTS FOR COVARIATES AND FACTORS TO BE INCLUDED IN ANALYSES

No statistical comparison will be conducted, so no adjustments for covariates and factors are to be considered.

Document:

PPD

Author:

PPD

Version Number:

1.0

Version Date:

06MAY2024

7.2. MULTICENTER STUDIES

This study will be conducted by multiple investigators at multiple centers in the US.

Center pooling will not be implemented in analyses for this study.

7.3. MISSING DATA

Individual missing items in any scale will not be imputed in any analysis. When calculating a total score, subscale score, or any summary scores based on more than one item, if one or more items are missing at a visit, then the associated summary score will be set to missing. For additional details, see the individual scale description sections.

- Handling of missing effectiveness data, if any, is described in Sections [16.10](#).
- Handling of missing safety data, if any, is described in Sections [17.3](#) and [17.8](#).
- See [APPENDIX 2](#) for details of handling incomplete/missing dates.

7.4. MULTIPLE COMPARISONS/ MULTIPLICITY

No statistical comparison will be conducted, so no multiplicity adjustment will be performed.

7.5. EXAMINATION OF SUBGROUPS

Subgroup analyses will be conducted for subjects as stated in Section [16.1](#) for PANSS, Section [16.2](#) for CGI-S, and Section [17.3.9](#) for Adverse Events.

The following subgroups will be assessed. The subgroup haloperidol (hal) equivalent doses will be based on appendix III of the protocol. For lumateperone, 5.5 mg is equivalent to 1 mg of haloperidol (Leucht-2020).

- Sex:

Document: PPD

Author: PPD

Version Number:

1.0

Version Date:

06MAY2024

- Female
 - Male
- Age group:
 - ≤40 years
 - >40 years
- Race (in 3 categories):
 - White (White)
 - Black (Black or African American)
 - Other (All other races combined)
- BMI (kg/m²) categories:
 - Underweight: <18.5 kg/m²
 - Normal: ≥18.5 to <25.0 kg/m²
 - Overweight: ≥25.0 to <30.0 kg/m²
 - Obese: ≥30.0 kg/m²
- Baseline patient type based on UPSM factor scores at Baseline ([Hopkins S. , Ogirala, Loebel, & Koblan, 2020](#)) (only used in the subgroup analysis of PANSS total score):
 - Type 1: Prominently Disorganized
 - Type 2: Prominently Negative
 - Type 3: Prominently Hostile
 - Type 4: Prominently Positive
 - Type 5: Prominently Affective

Subjects will be classified into one of 5 patient types based on their PANSS UPSM factor scores at Baseline. See [APPENDIX 9](#) for details of how the classification will be made.

- Primary Reason for Switch:

Document:

PPD

Author:

PPD

Version Number:

1.0

Version Date:

06MAY2024

- Side Effect
 - Lack of Efficacy
- Duration of Switch:
 - 2 weeks
 - 3 weeks
 - 4 weeks
 - 5 weeks
 - 6 weeks
- Type of Pre-switch Antipsychotic
 - Partial Agonist
 - Strong M1/H1 Antagonist
 - Strong D2/3 Antagonist
 - Sedating
 - Non-sedating
- Pre-switch AP Dose Level
 - <= 6 mg HAL equivalent
 - > 6 mg HAL equivalent
- Metabolic Status
 - Metabolic Syndrome
 - No Metabolic Syndrome

Document: PPD

Author: PPD

Version Number:

1.0

Version Date:

06MAY2024

- Reason for Clinical Discontinuation
 - Adverse Event
 - Lack of Efficacy

7.5.1. DERIVATION OF SUBGROUPS

Metabolic Status

If a male subject meets at least 3 out of 5 of the characteristics listed below, the subject is considered metabolically impaired at Baseline.

1. Baseline waist circumference \geq 102 cm
2. Baseline fasting triglycerides \geq 150 mg/dL (1.7 mmol/L) or use of drug treatment for elevated triglycerides at Baseline
3. Baseline fasting HDL $<$ 40 mg/dL (1.0 mmol/L) or use of drug treatment for reduced HDL at Baseline
4. (Baseline supine systolic blood pressure \geq 130 mmHg and/or Baseline supine diastolic blood pressure \geq 85 mmHg) or use of anti-hypertensive medications at Baseline
5. Baseline fasting glucose \geq 100 mg/dL or use of antidiabetic medications at Baseline

If a female subject meets at least 3 out of 5 of the characteristics listed below, the subject is considered metabolically impaired at Baseline.

1. Baseline waist circumference \geq 88 cm.
2. Baseline fasting triglycerides \geq 150 mg/dL (1.7 mmol/L) or use of drug treatment for elevated triglycerides at Baseline
3. Baseline fasting HDL $<$ 50 mg/dL (1.3 mmol/L) or use of drug treatment for reduced HDL at Baseline
4. (Baseline supine systolic blood pressure \geq 130 mmHg and/or Baseline supine diastolic blood pressure \geq 85 mmHg) or use of anti-hypertensive medications at Baseline
5. Baseline fasting glucose \geq 100 mg/dL or use of antidiabetic medications at Baseline

Document:	PPD	
Author:	PPD	Version Number: Version Date:

1.0
06MAY2024

8. OUTPUT PRESENTATIONS

[APPENDIX 1](#) shows conventions for presentation of data in outputs.

The templates provided with this SAP describe the presentations for this study and therefore the format and content of the summary tables, figures, and listings to be provided by IQVIA.

9. DISPOSITION AND WITHDRAWALS

Unless otherwise specified, the disposition summary tables will include the columns: SEP-363856 50 to 100 mg/day.

All subjects who were enrolled will be accounted for in this study.

The number and percentage of subjects who were screened, screen failed, enrolled in study SEP361-308, enrolled but did not receive study medication, received at least one dose of study medication, and completed or discontinued from the treatment period (including reasons for discontinuation) will be presented. In addition, the number and percentage of subjects who rolled over to the open-label extension study (SEP361-309) will be presented.

With respect to the above, the following definitions apply:

- Screened Subjects: Any subject who signed the study specific informed consent.
- Screen Failures: Any subject who signed the study specific informed consent but either failed to meet study requirements during screening or met study requirements at screening but was not dosed.

Subjects who were screened more than once will be counted only once in the disposition summary based on the outcome of the last screening. If a subject failed multiple screenings, they will only be counted once as a screen failure. If a subject is dosed after multiple screenings, they will only be counted once as an enrolled subject.

Discontinuation by visit will be summarized for the enrolled subjects.

The number and percentage of enrolled subjects will also be summarized by Site.

Lastly, the number and percentage of enrolled subjects included in and excluded from each analysis population will be summarized, along with the reason for exclusion.

Document: PPD

Author: PPD

Version Number:

1.0

Version Date:

06MAY2024

COVID-19 related analysis updates:

The number of subjects who failed screening due to COVID-19 related reasons, who discontinued early due to COVID-19 related reasons, and who completed the treatment period but did not roll over to the open-label extension study due to COVID-19 related reasons will be summarized in the disposition table.

Subjects affected by COVID-19 related study disruptions will be provided in data listings. These subjects will be identified as:

- *Subjects who failed screening due to COVID-19.*
- *Subjects who were enrolled but discontinued from the treatment period due to COVID-19.*
- *Subjects who completed the treatment period but did not roll over to the open-label extension study (SEP361-309) due to COVID-19.*
- *Subjects who experienced a pre-treatment event / adverse event related to COVID-19.*
- *Subjects who had any protocol deviations related to COVID-19.*
- *Subjects who had any investigator comments related to COVID-19.*

A subject may be identified in one or more categories listed above.

9.1. DERIVATIONS

- Time to discontinuation of the treatment in days.

For the purpose of this analysis, a subject's last dose date will be derived as follows:

- o If a subject's observed last dose date is before or on the date of Study Day 56, the derived last dose date will be set to the observed last dose date.
- o If a subject's observed last dose date is after the date of Study Day 56, the derived last dose date will be set to the date of Study Day 56.

Time to discontinuation (days) = Derived last dose date – First dose date + 1.

The event of interest is the discontinuation of treatment. Subjects who completed the treatment will be censored on the derived last dose date.

Document: PPD

Author: PPD

Version Number:

1.0

Version Date:

06MAY2024

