Abbreviations: AE = adverse event; BARS = Barnes Akathisia Rating Scale; β hCG = human chorionic gonadotropin; BMI = Body Mass Index; BNSS = Brief^f Negative Symptom Scale; C-SSRS = Columbia Suicide Severity Rating Scale; eCRF = electronic case report form; EDC = electronic data capture; DSM-5 = Diagnostic and Statistical Manual of Mental Disorders – Fifth Edition; EOT = end of treatment; ET = early termination; FSH = Follicle stimulating hormone; MSQ = Medication Satisfaction Questionnaire; PANSS = Positive and Negative Syndrome Scale; PSP = Personal and Social Performance Scale; PK = pharmacokinetic; PSQI = Pittsburgh Sleep Quality Index; SAS = Simpson-Angus Scale; SCID-5-CT = Structured Clinical Interview for DSM-5; SF-12 = Short Form Health survey; Clinical Trials Version; TC = telephone contact visit; UDS = urine drug screen.

^a. Subjects who screen fail can be re-screened up to 2 times after consultation with the Medical Monitor. Screening assessments may occur over multiple days. The Screening Period may be extended for up to 7 days after approval from the Medical Monitor.

^b. All procedures and assessments scheduled for Week 8 will be utilized as Baseline procedures and assessments for the open-label extension study (SEP361-309).

^c. If a subject discontinues from the study, all Early Termination (ET) procedures should be performed at the ET visit, within 48 hours of last study dose.

^d. Subjects who discontinue early from the study or complete the study and do not enter the extension study (SEP361-309) will have a safety Follow-up Visit 7 (\pm 2) days after their last dose of study drug. While every effort should be made to complete the Follow-up Visit in the clinic, administration of C-SSRS, and collection of AEs, and concomitant medications may occur by telephone contact if the subject is unable to come to the clinic for the Follow-up Visit.

^e. Visit window for Day 8 is +2 days and visit windows post Day 8 are \pm 2 days for every Visit.

^f. Requested, but not required for study participation.

- g. All study drug will be taken once daily in the evening at bedtime by mouth, without regard to food.
- h. The SCID-5-CT will be used to support the DSM-5 diagnosis and must be administered by a qualified rater with at least 2 years' experience with the population under study.
- i. Vital signs will include respiratory rate, oral body temperature and supine and standing measurements of blood pressure and pulse rate.

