Informed consent will be obtained from each subject before any study procedures are performed. Subjects will be evaluated for eligibility during a Screening Period of up to 21 days, during which they will continue on their pre-switch antipsychotic medication while being tapered off any prohibited medications ([Section 10.3.2](#)) in a manner that is consistent with labeling recommendations and conventional medical practices. Non-prohibited psychotropic medications other than the pre-switch antipsychotic may be continued during the study but must have been stable for at least 6 weeks prior to Screening and should be maintained at a stable dose and regimen (see [Section 10.3.1](#)).

Subjects who are being treated with two antipsychotic medications will be permitted to enter the Screening Period. At the start of Screening, the Investigator will determine which antipsychotic medication is considered “primary”, and the other one will be tapered off during the Screening Period.

Subjects who screen fail may be re-screened twice, if judged appropriate by the Investigator after discussion with the Medical Monitor. Re-screened subjects will be re-consented, assigned a new subject number, and all Visit 1 procedures will be repeated.

Open-label Treatment Period (8 weeks):

At Baseline (Day 1) (pre-switch [PS] Baseline), subjects who have successfully completed Screening and have met the eligibility criteria will begin open-label treatment with SEP-363856 while continuing to take the full dose of their pre-switch antipsychotic. SEP-363856 dosing will begin the evening of the PS Baseline visit and will continue once-daily, in the evening at bedtime, for the remainder of the Treatment Period, during which the procedures outlined in [Table 2](#) will be conducted. Subjects will be evaluated at PS Baseline and weekly throughout the rest of the study. [Section 10.3](#) describes the circumstances and specifications for which prior and concomitant psychotropic medications other than the pre-switch antipsychotic are allowed in this study.

Subjects will receive SEP-363856 50 mg/day from Day 1 through Day 3 and 75 mg/day from Day 4 through Day 7. Every effort should be made to maintain subjects at 75 mg/day from Day 4 through Day 7. Beginning on Day 8, the dose of SEP-363856 can be adjusted in increments of 25 mg among 3 dose levels (50, 75 and 100 mg), according to the following requirements:

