11.9.8. Visit 8 (Week 6; Day 43 \pm 2 days) – Treatment Period

The following procedures will be conducted during this visit:

- Collect concomitant medications
- Vital sign measurements
- PANSS
- CGI-S
- CGI-I
- C-SSRS
- Collect adverse events

- Study drug accountability
- Dispense study drug

11.9.9. Visit 9 Telephone Contact (Week 7; Day 50 ± 2 days) – Treatment Period

The following procedures will be conducted during this visit:

- Collect concomitant medications
- C-SSRS
- Collect adverse events

11.9.10. Visit 10, End of Treatment (EOT) or Early Termination (ET) - (Week 8; Day 57 ± 2 days)

The following procedures will be conducted during this visit:

- Collect concomitant medications
- Collect nicotine use information
- Physical and neurological examination
- Vital sign measurements
- Weight and waist circumference (BMI derived in the electronic data system)
- Perform standard 12-lead ECG
- Fasted blood samples for clinical laboratory evaluation (hematology and serum chemistry) and β -hCG (for female subjects)
- Blood sample for POPPK
- Urine sample for urinalysis, rapid urine β -hCG (females), rapid urine drug screen, and UDS
- PANSS
- CGI-S
- CGI-I
- BNSS
- PSQI
- C-SSRS
- SAS
- BARS
- AIMS
- SF-12
- MSQ

- PSP
- HCRU (since last visit)
- Collect adverse events
- Study drug accountability
- Duplicate subject check

At this visit, subjects who have participated throughout the duration of the Treatment Period, up to and including Week 8 will have the option to enroll and continue treatment in an open-label extension study (Study SEP361-309).

For subjects entering the extension study, the Week 8 Visit in this study (SEP361-308) will serve as the OLE Baseline visit for the extension study (SEP361-309) and subjects will not need to return for further visits in this study.

Subjects who do not enter the extension study will complete the Follow-up Period.

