17.1. DISCONTINUATION DUE TO CLINICAL REASONS

Discontinuation for clinical reasons is defined as reasons due to AE or lack of efficacy. AE will follow the definition as in section [17.3](#).

The percentage of subjects who discontinued for clinical reasons will be calculated by a proportion consisting of the number of subjects who experience a discontinuation event due to clinical reasons as the numerator divided by the number of subjects in the safety population as the denominator multiplied by 100 along with a corresponding 95% confidence interval (CI).

The number and percentage of subjects, who discontinued early from the open-label treatment period (including both clinical reasons, ie, discontinued due to an AE or lack of efficacy (primary endpoint) and any reason for discontinuation (secondary endpoint)) will be presented.

The time-to-discontinuation for clinical reasons will be summarized descriptively, (eg, n, median, 25th percentile, 75th percentile, minimum and maximum, and 95% CI on median, where possible).

Time to discontinuation for clinical reasons since first dose of study medication will be plotted using Kaplan-Meier curves for the safety population by treatment group. Probability of remaining on treatment at Day 56, median time to discontinuation, and their 95% confidence intervals will be estimated using the Kaplan-Meier method for the safety population by treatment group.

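### SAP 9.1 censors completers with an early in-window Week 8 visit on Day 54 or 55, so the exploratory all-cause Kaplan-Meier estimate at Day 56 can exceed the crude secondary endpoint

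*SAP*

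**What the plan says.** SAP 9.1 derives a last dose date for the time-to-discontinuation analysis in two steps. An observed date that "is before or on the date of Study Day 56, the derived last dose date will be set to the observed last dose date". One that "is after the date of Study Day 56, the derived last dose date will be set to the date of Study Day 56". Both steps apply to every subject. The event is discontinuation of treatment, and "Subjects who completed the treatment will be censored on the derived last dose date". No step moves an early completer forward to Day 56.

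SAP 17.1 then asks for this output: "Probability of remaining on treatment at Day 56, median time to discontinuation, and their 95% confidence intervals will be estimated using the Kaplan-Meier method". SAP 17.2 repeats the analysis for discontinuation for any reason. It stands beside the crude percentage of the safety population, which is the secondary endpoint.

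The protocol sets the timing. Section 11.9.10 places Visit 10 at "Week 8; Day 57 ± 2 days", which is Days 55 to 59. Section 7.1 says "SEP-363856 dosing will begin the evening of the PS Baseline visit and will continue once-daily, in the evening at bedtime". Protocol Table 4 counts as completed a subject who took part up to and including Week 8, with no minimum number of dosing days. SAP 6.5 applies no visit windowing. Protocol 15.3.5.1 calls the time-to-discontinuation analysis exploratory.

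**The concern.** With bedtime dosing, the last dose before a clinic visit is normally taken the evening before. A Week 8 visit on Days 55 to 59 therefore goes with a last dose on Days 54 to 58. Completers seen on Day 55 or 56 followed the protocol and are known not to have discontinued, yet the rule removes them from the risk set on Day 54 or 55 as if their Day 56 status were unknown.

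For all-cause discontinuation only completers are censored, so 1 - KM(Day 56) ought to reproduce the secondary percentage. Under the written rule it can equal or exceed that percentage but never fall below it. The clinical study report could then show two different 8-week all-cause rates for the same subjects, and the gap would come only from visit scheduling.

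**Working it through.** **The plan's own figures.** The documents give no Kaplan-Meier figure to reproduce. The nearest stated figure is the precision in SAP 3.4: 1.96 × sqrt(0.072 × 0.928 / 100) = 5.07%, which matches the stated 5.1% and is not in dispute.

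**Inputs from the documents.** N = 101 enrolled (SAP 3.4), taken as the safety population; Visit 10 on Days 55-59; evening dosing; the SAP 9.1 rules.

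**Assumptions not in the documents.**
- D = 20 all-cause discontinuations (10 and 30 also tried).
- A share f of completers with last dose on Day 54-55. If visits were uniform over the five-day window, f = 2/5 = 40%; 20% to 80% were tried.
- k non-completers with derived time Day 56, k = 0 to 3.

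**Formula.** Let e be the number of early completers. Before Day 56 there are D - k events, all taken to precede the first censoring on Day 54. A subject censored on an event day stays in that day's risk set. Then

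S(56) = [(N - D + k)/N] × [(N - D - e)/(N - D + k - e)].

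If k = 0 or e = 0 this reduces to (N - D)/N, so 1 - S(56) = D/N, the crude percentage.

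**Numbers for D = 20** (81 completers; crude 20/101 = 19.80%). At f = 40%, e = 32:
- k = 1: (82/101) × (49/50) = 0.7956, so 20.44%
- k = 2: (83/101) × (49/51) = 0.7896, so 21.04%
- k = 3: (84/101) × (49/52) = 0.7837, so 21.63%

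| Early completers | k = 0 | k = 1 | k = 2 | k = 3 |
|---|---|---|---|---|
| 0% | 19.80 | 19.80 | 19.80 | 19.80 |
| 20% (e = 16) | 19.80 | 20.04 | 20.27 | 20.50 |
| 40% (e = 32) | 19.80 | 20.44 | 21.04 | 21.63 |
| 60% (e = 49) | 19.80 | 21.27 | 22.66 | 23.96 |
| 80% (e = 65) | 19.80 | 23.59 | 26.95 | 29.96 |

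The excess over crude at 20-40% early completers is 0.24 to 1.83 points. With D = 10 or D = 30 the differences are almost the same (at 40% and k = 1, 0.64 and 0.63 points). A single event on Day 55 instead of Day 56, at 40%, gives 20.04%, an excess of 0.24.

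**Interval width.** The crude half-width is 1.96 × sqrt(0.198 × 0.802 / 101) = 7.8 points. Greenwood's formula at 40% gives:
- k = 1: 1.96 × 0.7956 × sqrt[19/(101 × 82) + 1/(50 × 49)] = 8.1 points
- k = 3: 1.96 × 0.7837 × sqrt[17/(101 × 84) + 3/(52 × 49)] = 8.7 points

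**Role of the cap.** The 0% row shows that the cap alone produces no excess. Without it, a last dose on Day 57 would drop out of the Day 56 estimate, which for k = 1 would be 19/101 = 18.81%.

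**After the fix.** Censoring all completers at Day 56 means e = 0. The estimate then equals D/N in every scenario: 9.90%, 19.80% and 29.70% for D = 10, 20 and 30.

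**The case against.** The strongest reply is that the triggering event should be uncommon. It needs a non-completer whose last dose falls on Day 55 or later. Protocol Table 2, footnote c, asks for the early termination visit within 48 hours of the last dose. Someone dosed on Day 56 would therefore be seen by Day 58, inside the Week 8 window and at the same Visit 10, and would normally count as a completer. What remains is chiefly a subject who takes the final doses and then misses or refuses the last visit. This stands, and zero such events is a plausible outcome. The event is not excluded, however: Visit 9 is a telephone contact, no drug is dispensed after Day 43, and SAP 9.1 itself provides for last doses after Day 56.

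It also stands that the analysis is exploratory, and that no test, decision rule or sample size uses the Kaplan-Meier value.

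A further reply is that censoring at the last observed dose is ordinary practice, and that the change credits 56 days to someone last dosed on Day 54. For exposure that would matter, but SAP 14.1 derives exposure separately from the actual dates. For a discontinuation landmark, the completer's status is known.

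A reader might infer that the Day 56 estimate is always too high, or that the cap on late discontinuations causes the excess. The documents support neither: without an event on Day 55-56 the figures coincide, and the cap applies to all subjects and adds nothing over the crude rate.

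**Conclusion.** The point holds in a conditional form. Completers with an early in-window Week 8 visit are censored before the landmark although known not to have discontinued. If at least one non-completer has a derived time on Day 55 or 56 after such censoring, the all-cause 1 - KM(Day 56) will exceed the secondary percentage. The excess is about 0.2 to 1.8 points for one to three such events with 20-40% early completers, assuming n = 101 and 20 discontinuations, against a half-width of about 7.8 points. It becomes large only if most completers are seen early.

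A reader might also infer that the primary or secondary endpoint is biased. It is not: both are crude proportions of the safety population and do not use these times. No size is given for the clinical-reasons curve, because the SAP does not say how discontinuations for other reasons enter it.

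Severity: minor.

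**What to change.** In SAP 9.1, state that subjects who completed the treatment period are censored at Day 56, whatever their observed last dose date. Keep the Day 56 cap for subjects who discontinued. As a programming check, require that the all-cause 1 - KM(Day 56) equals the secondary endpoint percentage in the safety population.

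The cost is one sentence and one line of code. It needs no new data and changes no endpoint.
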